## 1. Protocol Synopsis

### Title of Study:

A Phase 4 Study to Evaluate Glucodynamic Effects of Dulaglutide in Japanese Patients with Type 2 Diabetes Mellitus.

### Rationale:

In the clinical development program of dulaglutide in Japan, meal tolerance test (MTT) after administration of 0.75 mg of dulaglutide in patients with type 2 diabetes mellitus (T2D) was not performed. Furthermore, postprandial glucose metabolic hormones after administration of 0.75 mg of dulaglutide were not assessed. These data are frequently requested by healthcare providers.

Study GBGK will evaluate detailed 4-hour postprandial data at 1, 2, and 4 weeks after starting administration of 0.75 mg of dulaglutide once weekly, and these data will provide information not collected in previous studies for dulaglutide in Japanese patients with T2D.

### Objectives/Endpoints:

Objectives	Endpoints

Primary
 
The primary objective of this study is to evaluate glucodynamic effects of dulaglutide 0.75 mg compared with placebo in area under the glucose concentration versus time curve from 0 to 4 hours (glucose AUC[0-4h]) at 4 weeks in Japanese patients with T2D.
	
 
The change from baseline in glucose AUC(0-4h) at 4 weeks
 

Secondary
 
To evaluate pharmacodynamic (PD) effects of dulaglutide 0.75 mg compared with placebo at 4 weeks.
	
 
The change from baseline in fasting blood glucose at 4 weeks
 
The change from baseline in postprandial blood glucose at 4 weeks
 
The change from baseline in insulin at 4 weeks
 
The change from baseline in c-peptide at 4 weeks
 
The change from baseline in glucagon at 4 weeks
 
The change from baseline in triglyceride at 4 weeks
 

To evaluate safety and tolerability of dulaglutide 0.75 mg for 4 weeks.
	
 
Treatment-emergent adverse events (TEAEs)
 
Incidence of hypoglycemic episodes
 

### Summary of Study Design:

Study GBGK is a Phase 4, single-center, randomized, cross-over, single-blind, placebo-controlled study to evaluate glucodynamic effects of dulaglutide in Japanese patients with T2D after a standardized test meal.

### Treatment Arms and Planned Duration for an Individual Patient:

Two cohorts of dulaglutide 0.75 mg → placebo or placebo → dulaglutide 0.75 mg.

The patient will be randomized in a 1:1 ratio to dulaglutide 0.75 mg → placebo or placebo → dulaglutide 0.75 mg.

Ten- to 28-day screening period.

Cross-over design with 4 weeks' treatment and additional 4 weeks' cross-over treatment after 4 to 6 weeks' washout period.

**Number of Patients:**

Up to 14 patients may be entered to randomize 12 patients and complete at least 11 patients.

**Statistical Analysis:**

The PD parameters on Weeks 0, 1, 2, and 4 will be analyzed using a mixed-effects linear model. The PD parameters for glucose, insulin, glucagon, c-peptide, and triglyceride that will be statistically evaluated include area under the curve, fasting and postprandial values at each time point. The model will include treatment, sequence, day, and treatment-by-day interaction as fixed effects, baseline as covariate, and patient as random effect. The baseline is the predose value on Day 1. The least squares means and the 95% confidence intervals (CIs) by treatment group will be tabulated and plotted. Comparisons between dulaglutide and placebo will be performed. Difference of least squares means of dulaglutide to placebo, and the 95% CIs, will be tabulated.

## 2. Schedule of Activities

**Study Schedule Protocol H9X-JE-GBGK(a)**

Visit Number	Screening	CGM Initiation	Period 1 (4 weeks)					Washout (4-6 weeks)	CGM Initiation	Period 2 (4 weeks)					E/T i
	1	2	3	4	5	6	7	8	9	10	11	12	13	ET	
Study Day	-28~-10	-7 or -6	1	8	15	22	29	30~56	50 or 51	57 (1)	64 (8)	71 (15)	78 (22)	85 (29)	
Allowance (days)				±1	±1	±1	±1	+14			±1	±1	±1	±1	
Informed Consent	X														
Medical History	X														
Concomitant Medications	X	X	X	X	X	X	X			X	X	X	X	X	X
Adverse Events		X	X	X	X	X	X		X	X	X	X	X	X	X
Hypoglycemia		X	X	X	X	X	X		X	X	X	X	X	X	X
Height	X														
Weight a	X		X				X			X				X	X
Physical Exam	X	X	X	X	X	X	X			X	X	X	X	X	X
Vital Signs (sitting) b	X	X	X	X	X	X	X			X	X	X	X	X	X
ECG	X		X							X					
Pregnancy Test c	X	X	X							X					
Fasting Blood Glucose d	X														
Serology	X														
Hematology, Clinical Chemistry, Endocrinology, HbA1c d	X		X				X			X				X	X
Urinalysis, UACR d			X				X			X				X	X
MTT e			X	X	X		X			X	X	X		X	X j
Satiety Evaluation (VAS) f			X	X	X		X			X	X	X		X	X j
Continuous Glucose Monitoring g		←————→							←————→						
Investigational Product Administration h			X	X	X	X				X	X	X	X		

Abbreviations: ECG = electrocardiogram; E/T = early termination visit; HbA1c = glycated hemoglobin; UACR = urine albumin/creatinine ratio; MTT = meal tolerance test; VAS = visual analog scale.

- a Body weight will be measured once in light clothing with shoes removed.
- b For each parameter (systolic blood pressure, diastolic blood pressure, and pulse rate), 3 measurements will be taken 1 minute apart using the same arm. An appropriately sized cuff (cuff bladder encircling at least 80% of the arm) should be used to ensure the accuracy of blood pressure (BP) measurements. The arm used for the BP measurement should be supported at heart level. See [Appendix 6](#), Meal Tolerance Test, for details.
- c Serum pregnancy test will be performed at Visit 1. Urine pregnancy test will be performed at Visit 2, 3, and 9, if applicable.
- d Fasting condition. See [Appendix 2](#), Clinical Laboratory Tests, and [Appendix 6](#), Meal Tolerance Test, for details.
- e Blood sampling for glucose, insulin, c-peptide, glucagon, and triglyceride will occur at 0, 30, 60, 90, 120, 180, and 240 minutes after the standardized test meal. See [Appendix 6](#), Meal Tolerance Test, for details.
- f Satiety will be assessed at 0, 60, 120, 180, and 240 minutes after the standardized test meal. See [Appendix 6](#), Meal Tolerance Test, for details.
- g Continuous glucose monitoring will be initiated on Day -7 (or -6) and Day 50 (or 51) and will end on Day 8 and Day 64.
- h Investigational product will be administered at study site after all examinations, including MTT, are completed. See [Appendix 6](#), Meal Tolerance Test, for details.
- i Patients discontinuing from the study prematurely for any reason should complete adverse event and other follow-up procedures.
- j Optional.

## 3. Introduction

### 3.1. Study Rationale

In the clinical development program of dulaglutide in Japan, meal tolerance test (MTT) after administration of 0.75 mg of dulaglutide in patients with type 2 diabetes mellitus (T2D) was not performed. Furthermore, postprandial glucose metabolic hormones after administration of 0.75 mg of dulaglutide were not assessed. These data are frequently requested by healthcare providers.

Study GBGK will evaluate detailed 4-hour postprandial data at 1, 2, and 4 weeks after starting administration of 0.75 mg of dulaglutide once weekly, and these data will provide information not collected in previous studies for dulaglutide in Japanese patients with T2D.

In addition, continuous glucose monitoring (CGM) will be performed in each study period in order to evaluate the glucodynamic effects of dulaglutide 0.75 mg during the first week.

### 3.2. Background

Dulaglutide exhibits glucagon-like peptide-1 (GLP-1) mediated effects, including glucose-dependent potentiation of insulin secretion, inhibition of glucagon secretion, delay of gastric emptying, and weight loss. Preclinical and clinical experience to date support the use of dulaglutide as a once-weekly injection to improve glycemic control in patients with T2D (Tamaki et al. 2015). Dulaglutide received regulatory approval for the treatment of T2D in the United States on 18 September 2014, in the European Union on 21 November 2014, and in Japan on 3 July 2015.

### 3.3. Benefit/Risk Assessment

This study will assess detailed plasma glucose (PG) profiles, insulin, c-peptide, glucagon, and triglyceride, and satiety after standardized test meal. These outcomes will be supportive data to understand the mechanism of action of dulaglutide, and to answer the frequently asked questions by healthcare providers.

For the patients participating in this study, there is no anticipated therapeutic benefit because of the short treatment period (4 weeks).

No clinically significant safety or tolerability concerns about dulaglutide 0.75 mg have been identified in patients to date.

More detailed information about the known and expected benefits and risks of dulaglutide 0.75 mg may be found in the Package Insert.

## 4. Objectives and Endpoints

Table GBGK.1 shows the objectives and endpoints of the study.

**Table GBGK.1. Objectives and Endpoints**

Objectives	Endpoints

Primary The primary objective of this study is to evaluate glucodynamic effects of dulaglutide 0.75 mg compared with placebo in area under the glucose concentration versus time curve from 0 to 4 hours (glucose AUC[0-4h]) at 4 weeks in Japanese patients with T2D.
	
 
The change from baseline in glucose AUC(0-4h) at 4 weeks
 

Secondary To evaluate pharmacodynamic (PD) effects of dulaglutide 0.75 mg compared with placebo at 4 weeks.
	
 
The change from baseline in fasting blood glucose at 4 weeks
 
The change from baseline in postprandial blood glucose at 4 weeks
 
The change from baseline in insulin at 4 weeks
 
The change from baseline in c-peptide at 4 weeks
 
The change from baseline in glucagon at 4 weeks
 
The change from baseline in triglyceride at 4 weeks
 

To evaluate safety and tolerability of dulaglutide 0.75 mg for 4 weeks
	
 
Treatment-emergent adverse events (TEAEs)
 
Incidence of hypoglycemic episodes
 

Tertiary/Exploratory Objectives To evaluate daily glucose variability
	
 
Time course of daily average glucose by CGM during the first week
 

To evaluate satiety after standardized test meal
	
 
The change from baseline in satiety (full and hungry) in visual analog scale (VAS) at 1, 2, and 4 weeks
 

## 5. Study Design

### 5.1. Overall Design

Study GBGK is a Phase 4, single-center, randomized, cross-over, single-blind, placebo-controlled study to evaluate glucodynamic effects of dulaglutide after standardized test meal in Japanese patients with T2D.

The study includes a 10- to 28-day screening period, a 4-week treatment period (Period 1), a 4- to 6-week washout period, and a 4-week treatment period (Period 2).

[figure not shown]
Screening tests will be performed at Visit 1. After confirming eligibility, the patient will be randomized in a 1:1 ratio to dulaglutide 0.75 mg or placebo treatment in Period 1.

Meal tolerance test will be performed at baseline, 1, 2, and 4 weeks for each period. Time points for blood sampling will be 0, 30, 60, 90, 120, 180, and 240 minutes after the start of standardized test meal. Satiety will be also assessed at 0, 60, 120, 180, and 240 minutes after the start of standardized test meal. Detailed schedule of MTT is described in [Appendix 6](#). After completion of Period 1, all patients must have a 4- to 6-week washout period, and then will start Period 2 on the opposite treatment (patients taking dulaglutide will be switched to placebo and patients taking placebo will be switched to dulaglutide).

This is a single-blind study, and the treatment assignments will be blinded to patients until study completion.

Study governance considerations are described in detail in [Appendix 3](#).

[Figure GBGK.5.1](#) illustrates the study design.

▲ Meal tolerance test (240 minutes at 0, 1, 2, 4 weeks)

Abbreviations: CGM = continuous glucose monitoring; dula = dulaglutide; n = number of patients.

**Figure GBGK.5.1. General study design for Protocol H9X-JE-GBGK.**

## 5.2. Number of Participants

Up to 14 patients may be entered to randomize 12 patients and complete at least 11 patients. For the purposes of this study, a patient completes the study when all scheduled procedures shown in the Schedule of Activities have been finished.

## 5.3. End of Study Definition

End of the study is the date of the last visit or last scheduled procedure shown in the Schedule of Activities (Section 2) for the last patient.

## 5.4. Scientific Rationale for Study Design

This study is designed to evaluate glucodynamic effects after standardized test meal. Cross-over design was selected to minimize the effect of confounding factors between patients. Placebo will be used to minimize the effect of bias including placebo effects. Duration of washout period (4 to 6 weeks) was set based on the results of Japan Phase 3 monotherapy study (GBDP). In the GBDP study, fasting blood glucose was returned to baseline 4 weeks after discontinuation of study drug. Patients with T2D who have diet and exercise therapy only will be enrolled to exclude background effect of other antidiabetic agents. Japanese standardized test meal (480 kcal, carbohydrate: protein: fat = 2.8:1:1) was selected because that was used in the previous MTTs conducted in Japan (Lee et al. 2010, Yabe et al. 2010, Yabe et al. 2015).

Japanese patients are leaner compared with the Western population and eat rice as their staple diet. As a result, insulin secretion in the Japanese is lower than that in the Western population, and postprandial glucose tends to be increased (Obika and Trence 2010). Therefore, reduction of postprandial glucose is relatively more important for Japanese patients compared with the Caucasian patients. Also, postprandial insulin, c-peptide, glucagon, and triglyceride data will be supportive data to consider the mechanism of action of this drug.

**5.5. Justification for Dose**

The approved dosage and administration of dulaglutide in Japan is 0.75 mg once weekly, given subcutaneously. The dosage and administration were established based on Phase 2 and 3 studies in Japanese patients with T2D (Terauchi et al. 2014, Araki et al. 2015, Emoto et al. 2015, Miyagawa et al. 2015, Odawara et al. 2016).

## 6. Study Population

Eligibility of patients for the study will be based on the results of screening medical history, physical examination, vital signs, clinical laboratory tests, and electrocardiogram (ECG).

The nature of any conditions present at the time of the physical examination and any preexisting conditions will be documented.

Screening may occur 10 to 28 days prior to enrollment. Patients who are not enrolled within 28 days of screening may be subjected to an additional medical assessment and/or clinical measurements to confirm their eligibility.

Prospective approval of protocol deviations to recruitment and enrollment criteria, also known as protocol waivers or exemptions, are not permitted.

### 6.1. Inclusion Criteria

Patients are eligible for inclusion in the study only if they meet all of the following criteria at screening and/or enrollment:

[1] are males or females ages of  $\geq 20$  and  $\leq 75$  years at Visit 1;

[1a] male patients:

- Men with partners of childbearing potential, for the duration of the study and for 120 days after the last dose of study drug, will either remain abstinent (if this is their preferred and usual lifestyle) or use at least one highly effective (less than 1% failure rate) method of contraception (such as combination oral contraceptives, implanted contraceptives, or intrauterine device) or an effective method of contraception (such as male or female condoms with spermicide, diaphragms with spermicide, or cervical sponges). The patient may choose to use a barrier method of contraception. Barrier protection methods without concomitant use of a spermicide are not an effective or acceptable method. Thus, each barrier method must include use of a spermicide. It should be noted, however, that the use of male and female condoms as a double barrier method is not considered acceptable due to the high failure rate when these barrier methods are combined.
- Men should refrain from sperm donation for the duration of the study and for 120 days after the last dose of study drug.
- Men who are in exclusively same sex relationships (when it is their preferred and usual lifestyle) are not required to use contraception.

[1b] female patients:

- 1) Women of childbearing potential who are abstinent (if this is complete abstinence, as their preferred and usual lifestyle) or in a same sex relationship (as part of their preferred and usual lifestyle) must agree to either remain abstinent or stay in a same sex relationship without sexual relationships with males.

- 2) Otherwise, women of childbearing potential participating must agree to use one highly effective method (less than 1% failure rate) of contraception, or a combination of two effective methods of contraception for the entirety of the study.
  - A. Women of childbearing potential must test negative for pregnancy prior to initiation of treatment as indicated by a negative serum pregnancy test at the screening visit followed by a negative urine pregnancy test within 24 hours prior to exposure.
  - B. Either one highly effective method of contraception (such as combination oral contraceptives, implanted contraceptives, or intrauterine device) or a combination of two effective methods of contraception (such as male or female condoms with spermicide, diaphragms with spermicide, or cervical sponges) will be used. The patient may choose to use a double barrier method of contraception. Barrier protection methods without concomitant use of a spermicide are not a reliable or acceptable method. Thus, each barrier method must include use of a spermicide. It should be noted that the use of male and female condoms as a double barrier method is not considered acceptable due to the high failure rate when these methods are combined.
- 3) Women not of childbearing potential may participate and include those who are:
  - A. infertile due to surgical sterilization (hysterectomy, bilateral oophorectomy, or tubal ligation) or congenital anomaly such as mullerian agenesis; or
  - B. postmenopausal – defined as either
    - i. A woman at least 50 years of age with an intact uterus, not on hormone therapy, who has had either
      - a) cessation of menses for at least 1 year, or
      - b) at least 6 months of spontaneous amenorrhea with a follicle-stimulating hormone  $>40$  mIU/mL; or
    - ii. A woman 55 years or older not on hormone therapy, who has had at least 6 months of spontaneous amenorrhea; or
    - iii. A woman at least 55 years of age with a diagnosis of menopause prior to starting hormone replacement therapy.
- [2] have T2D (based on the World Health Organization's [WHO] diagnostic criteria) for at least 1 year.
- [3] have diet and exercise therapy only (no oral antihyperglycemic medication for at least 3 months prior to Visit 1).
- [4] have a fasting blood glucose value of  $\geq 120$  and  $\leq 200$  mg/dL at Visit 1.
- [5] have a screening body weight of  $\geq 50$  and  $\leq 80$  kg.

- [6] are reliable and willing to make themselves available for the duration of the study and are willing to follow study procedures.
- [7] are able and willing to give signed informed consent.

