## Appendix 6. Meal Tolerance Test

Time	Procedure
-120 min	Physical exam, vital signs (sitting) Weight (only Day 1, Day 29, Day 57, and Day 85) ECG (only Day 1 and Day 57) Urine sampling for pregnancy test (only Day 1 and Day 57, if needed) Urinalysis and UACR (only Day 1, Day 29, Day 57, and Day 85) Blood sampling for hematology, clinical chemistry, endocrinology, HbA1c (only Day 1, Day 29, Day 57, and Day 85) Blood sampling for glucose, insulin, c-peptide, glucagon, and triglyceride (for 0 min) Satiety evaluation (VAS) (for 0 min)
0 min	Start standardized test meal a
30 min	Blood sampling for glucose, insulin, c-peptide, glucagon, and triglyceride
60 min	Blood sampling for glucose, insulin, c-peptide, glucagon, and triglyceride Satiety evaluation (VAS)
90 min	Blood sampling for glucose, insulin, c-peptide, glucagon, and triglyceride
120 min	Blood sampling for glucose, insulin, c-peptide, glucagon, and triglyceride Satiety evaluation (VAS)
180 min	Blood sampling for glucose, insulin, c-peptide, glucagon, and triglyceride Satiety evaluation (VAS)
240 min	Blood sampling for glucose, insulin, c-peptide, glucagon, and triglyceride Satiety evaluation (VAS)
After MTT	Dose of dulaglutide 0.75 mg or placebo (except Days 29 and 85)

Abbreviations: HbA1c = glycated hemoglobin; min = minutes; MTT = meal tolerance test; UACR = urine albumin/creatinine ratio; VAS = visual analog scale.

a Japanese standard test meal (480 kcal, carbohydrate: protein: fat = 2.8:1:1) should be ingested within 15 min.

---

**Appendix 7. Protocol Amendment H9X-JE-GBGK(a)  
Summary: A Phase 4 Study to Evaluate Glucodynamic  
Effects of Dulaglutide in Japanese Patients with Type 2  
Diabetes Mellitus**

---

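### Criterion [1b] 2) gives women of childbearing potential no contraception period counted from the last dose, while men are given 120 days and the difference is not explained

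*Protocol*

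**What the plan says.** Protocol section 6.1 sets different end dates for the two sexes. Under [1b] 2), women of childbearing potential must use one highly effective method or "a combination of two effective methods of contraception for the entirety of the study". Nothing is added for the time after the last dose. Under [1b] 1), women who are abstinent or in a same-sex relationship must agree to remain so, and no end date is given. Under [1a], men with partners of childbearing potential are bound "for the duration of the study and for 120 days after the last dose of study drug", and the same 120 days applies to sperm donation.

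Two definitions bear on when the women's obligation ends. Section 5.2 says that "a patient completes the study when all scheduled procedures shown in the Schedule of Activities have been finished". Section 5.3 says "End of the study is the date of the last visit or last scheduled procedure shown in the Schedule of Activities" for the last patient.

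On testing, footnote c of the Schedule of Activities has a serum pregnancy test at Visit 1 and then: "Urine pregnancy test will be performed at Visit 2, 3, and 9, if applicable". Visit 9 is Day 57, and Appendix 6 agrees that Days 1 and 57 are the only meal-test days with a urine test. None is scheduled on Day 85 or at early termination. Section 9.2.1 routes any pregnancy through the SAE reporting process. It does not require investigators to look for events once a patient has completed or left the study.

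**The concern.** The protocol sets a post-dose period for the partners of treated men but not for women who receive the drug themselves. Because this is a crossover, the omission matters mainly for one sequence. Women randomized to placebo first receive dulaglutide in Period 2, and the schedule ends one week after their last injection. A woman who follows the criterion exactly could stop contraception at the Week 4 visit, where the primary drug effect is measured, with no later pregnancy test scheduled. What is at stake is patient and fetal safety. The estimate, the power and the primary analysis are not touched.

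**Working it through.** **Inputs.** From the Schedule of Activities and Appendix 6: injections on Days 1, 8, 15 and 22 (Period 1) and Days 57, 64, 71 and 78 (Period 2); no injection on Day 29 or Day 85; last scheduled visit Day 85; allowance of ±1 day on the visits after Day 1 of each period; +14 days on the washout. From section 5.1: placebo-first patients receive dulaglutide in Period 2. From section 10.1: 12 randomized, 1:1.

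1. **The plan's own figure.** Washout = 57 − 29 = 28 days (4 weeks), or 28 + 14 = 42 days (6 weeks) with the allowance. This reproduces the 4 to 6 weeks in section 5.1, so the day numbering is being read correctly.

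2. **Placebo-first, obligation ends at her own completion (section 5.2).** Last dulaglutide dose to final visit = 85 − 78 = 7 days. With windows: shortest 84 − 79 = 5, longest 86 − 77 = 9. A longer washout moves all of Period 2 together and does not change this.

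3. **Placebo-first, obligation ends at the last patient's last visit (section 5.3).** Interval = 7 + D, where D is the number of days from her final visit to that of the last patient. D depends on enrollment timing, which the documents do not give. For the last finisher D = 0, so the interval is again 7 days.

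4. **Early termination on dulaglutide.** The early termination visit has no study day tied to the last dose. If the obligation ends with her own participation, the interval is unset.

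5. **Dulaglutide-first.** Last dulaglutide dose to final visit = 85 − 22 = 63 days (shortest 84 − 23 = 61; longest 100 − 21 = 79 with the +14 washout allowance). Completers in this sequence are not the problem.

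6. **Pregnancy testing.** The last test is on Day 57, before that day's injection. For a placebo-first woman this is before her first dulaglutide dose, 78 − 57 = 21 days before her last dose and 85 − 57 = 28 days before her final visit.

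7. **Number affected.** The placebo-first sequence has about 12 / 2 = 6 patients. No sex or age split is given, so the range on the section 5.2 reading is 0 to about 6. Early terminators on dulaglutide in the other sequence could add to this.

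8. **Other intervals in the protocol, as context only.** The washout is 4 to 6 weeks, which makes 57 − 22 = 35 days from the last Period 1 dose to Period 2 (49 with the allowance). Section 5.4 bases it on the finding that "fasting blood glucose was returned to baseline 4 weeks after discontinuation of study drug". Exclusion [11] uses 30 days, or 5 half-lives if longer, after a previous investigational product. Section 6.3.3 bars blood donation for 4 weeks after the study. Men have 120 days. None of these was set as a contraception period for women.

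**The case against.** The strongest objection is that the documents do not show that 7 days is too short. A reader might infer from the washout that 35 days is the protocol's standard and that 7 days fails it. The text does not support that. The washout was set on the return of fasting glucose to baseline and protects the Period 2 comparison from carry-over. It says nothing about elimination or reproductive risk. Exclusion [11] is closer in kind but concerns products from other trials, and no half-life for dulaglutide is given to apply it with. This objection stands, and no length is derived here.

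A reader might also infer that every placebo-first woman may stop at 7 days. That takes the section 5.2 reading. Section 5.3 is the only definition of the end of the study, and under it all but the last finishers could be bound longer. This stands too, but it does not remove the gap: the wording is ambiguous, one reading gives 7 days, and the other makes a safety obligation depend on when other patients enrolled.

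The comparison with men is partial. Women face stricter method rules (one highly effective or two effective methods, against one effective method for men) and are tested for pregnancy before dosing. Those are real protections, but they do not set an end date after the last dose.

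Finally, consent pages were not available for this review, nor was the Package Insert to which section 3.3 refers. Either could contain a post-dose instruction or a reason for the difference. So it cannot be said that women have no post-dose protection at all, only that the criterion gives none. If the instruction exists elsewhere, the criterion should still carry it.

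**Conclusion.** The point holds as a gap in a stated rule. Criterion [1b] 2) counts nothing from the last dose, and its end point can be read in two ways. On the section 5.2 reading the interval for placebo-first completers is 7 days (5 to 9). On the section 5.3 reading it is 7 days plus an unguaranteed extension, and exactly 7 days nominally for the last finisher. Women who stop early on dulaglutide have no set interval on the first reading. The number affected is 0 to about 6 of 12 among placebo-first patients, and possibly only the last finisher, or nobody, on the second reading.

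The conclusion rests on the scheduled days and windows and on the protocol text available. It does not rest on any assumed half-life, and it makes no claim about the size of fetal risk. It is a worthwhile, low-cost safety improvement.

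**What to change.** Amend [1b] 2) so that the obligation runs through the study and then for a fixed number of days, X, counted from the last dose of study drug. Give [1b] 1) the same end date, state the reason for any difference from [1a], and carry the wording into the consent form. Counting from the last dose settles the choice between sections 5.2 and 5.3 and covers early terminators.

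X should be set by the sponsor's medical team from the drug's elimination: at least the longer of 30 days or 5 half-lives, borrowing the rule in exclusion [11]. The men's 120 days is a ready default. With X = 30 the obligation would end on Day 78 + 30 = Day 108, which is 23 days after the final visit. With X = 120 it would end on Day 198, which is 113 days (about 16 weeks) after it.

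The cost is protocol and consent wording, re-consent of any women already enrolled, and some weeks of added commitment for a few women. Because patients are blinded, the rule must also bind dulaglutide-first women, who are already nominally 63 days past their last dulaglutide dose at Day 85. No visit follows Day 85, so the added period would rest on the patient's agreement, as the men's 120 days already does.
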